7.3.2.2 Progression-Free Survival and Time to Progression

PFS is defined as the time from first dose of study medication to the first observation of disease progression or death. Progression is defined as the development of T2 or greater disease, which includes lymph node disease and distant metastasis.

Kaplan-Meier methods will be used to estimate the PFS (ie, percent surviving without a PFS event) and the 95% confidence interval at 48, 72, and 96 weeks in all patients in the FAS and the subgroup of patients with CIS. The median PFS and its 95% confidence interval will also be estimated. Kaplan-Meier plots for PFS will be created.

A sensitivity analysis of PFS will also be performed, which also includes an increase in stage from Ta or CIS to T1 as a progression event.

Time to progression is defined as first dose of study medication to the first observation of disease progression. Patients without a progression event (including death) will have their event time censored at the last progression-free disease assessment. All analyses performed for PFS, including all sensitivity analyses, will be performed for time to progression.

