#### **9.4.3 Maintenance Treatment**

Upon completion of the induction phase, patients will transition to a maintenance therapy schedule of BC-819 (ie, once every 3 weeks). The first maintenance treatment and visit will occur 12 weeks after enrollment (Visit 11). Treatments will continue every 3 weeks for 84 additional weeks until the end of the study (end of study [EOS] Visit 39) at 96 weeks.

Patients who have recurred with high-grade papillary carcinoma or with metastatic disease will be considered treatment failures and will be withdrawn from the study. All suspected recurrences (by direct visualization) must be documented by biopsy results.

Patients who are free of high-grade tumors or who are tumor-free (ie, patients benefiting from treatment) will be allowed to continue to receive maintenance therapy every 3 weeks per the schedule of treatment during the maintenance phase ([Table 12.2](#) and [Table 12.3](#)) as long as response status is maintained and they are not considered a treatment failure.

Patients will undergo repeat direct visualization (ie, cystoscopy  $\pm$  biopsy and cytology) and re-TUR (as needed for cause) every 12 weeks during the first and second year of the study.

All enrolled patients will complete the following quality of life questionnaires at the visits indicated in the study schedule ([Table 12.1](#) and [Table 12.2](#)):

- The European Organization for Research and Treatment of Cancer quality of life Questionnaire (EORTC QLQ-C30; a general questionnaire for cancer)
- Quality of Life Questionnaire–Non-Muscle-Invasive Bladder Cancer Questionnaire (QLQ-NMIBC24; a specific questionnaire for NMIBC disease)

The end of the study will be the 96-week visit (Visit 39) for all patients.

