### **13.5.3 Secondary Efficacy Analyses**

The secondary efficacy endpoints include the following:

- The incidence of EFS at 48 weeks, where EFS is defined as high-grade recurrence-free survival (overall population and subgroup of patients with CIS)
- The incidence of EFS at 12, 24, 36, 72, and 96 weeks, where EFS is defined as high-grade recurrence-free survival (overall population and subgroup of patients with CIS)
- Time to recurrence; recurrence is defined as an EFS event
- The incidence of PFS at 48, 72, and 96 weeks as well as time to progression estimated using Kaplan-Meier methods. Progression is defined as the development of T2 or greater disease. Sensitivity analyses will also be performed and will include any of the following as progressions:
  - An increase in stage from Ta or CIS to T1, or
  - Development of T2 or greater, or
  - Lymph node disease, or
  - Distant metastasis
- Overall survival of patients enrolled in the study at 48, 72, and 96 weeks and survival time estimated using Kaplan-Meier methods
- Changes in quality of life over time, as measured by EORTC QLQ-C30 and QLQ-NMIBC24

Additionally, patients with appearance of new high-grade disease (ie, new high-grade papillary disease in patients with CIS only or new CIS in patients with papillary disease only) will be classified as treatment failures, as will patients with CIS at baseline whose CIS lesions have not resolved by the 12-week cystoscopy.

Any patient without tumor in the bladder but presence of tumor in the upper urinary tract will not be classified as failures in these analyses and will continue study participation.

Rates will be summarized using two-sided 95% confidence intervals (using Kaplan-Meier estimates incorporating censoring for PFS and overall survival and both Kaplan-Meier estimates and exact binomial methods for EFS). Time to recurrence and other endpoints will be examined using Kaplan-Meier methods, with plots for the entire patient population, for subgroups of patients with papillary lesions only, and for patients with CIS (with or without papillary lesions). Time 0 is the time of first treatment with BC-819.

Further sensitivity and subgroup analyses will be described in the statistical analysis plan.

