5.1.2 Secondary Efficacy Endpoints

The secondary efficacy endpoints include the following:

- The incidence of event-free survival (EFS) at 48 weeks, where EFS is defined as high-grade recurrence-free survival (overall population and subgroup of patients with CIS)
- The incidence of EFS at 12, 24, 36, 72, and 96 weeks, where EFS is defined as high-grade recurrence-free survival (overall population and subgroup of patients with CIS)
- Time to recurrence; recurrence is defined as an EFS event
- The incidence of PFS at 48, 72, and 96 weeks as well as time to progression estimated using Kaplan-Meier methods. Progression is defined as the development of T2 or greater disease. Sensitivity analyses will also be performed and will include any of the following as progressions:
 - An increase in stage from Ta or CIS to T1, or
 - Development of T2 or greater, or
 - Lymph node disease, or
 - Distant metastasis
- Overall survival of patients enrolled in the study at 48, 72, and 96 weeks and survival time estimated using Kaplan-Meier methods
- Changes in quality of life over time, as measured by the EORTC QLQ-C30 (a general questionnaire for cancer) and the QLQ-NMIBC24 (a specific questionnaire for NMIBC disease)

This document is confidential.

Additionally, patients with appearance of new high-grade disease (ie, new high-grade papillary disease in patients with CIS only or new CIS in patients with papillary disease only) will be classified as treatment failures in EFS analyses, as will patients with CIS at baseline whose CIS lesions have not resolved by the 12-week cystoscopy, or who have recurrent CIS at later cystoscopies.

At each follow-up visit, response of existing lesions and presence of any new lesions will be evaluated (by direct visualization and biopsies as needed) and reported in the eCRF. Recurrences must be proven and documented by biopsy.

A biopsy will be performed at screening and when indicated by direct visualization at other visits for purposes of staging and grading.

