7.3.2.1 Event-Free Survival and Time to Recurrence

EFS is defined as the time from first dose of study medication to the first recurrence of disease or death from any cause. Recurrence of disease is defined as

- Appearance of new high-grade disease (ie, new high-grade papillary disease or new CIS) or
- Failure to clear CIS lesions by Week 12 cystoscopy in patients with CIS at baseline

Recurrence must be biopsy proven. Persistence, appearance, or presence of lower grade disease will not be considered recurrence in the primary EFS analyses. Sensitivity analyses will be performed with lower-grade disease also considered an EFS event.

Any patient without tumor in the bladder but presence of urothelial carcinoma in the upper urinary tract or prostatic urethra will not be classified as failures in these analyses and will continue study participation.

Additionally, the overall proportion of patients who have high grade recurrence (and subcategories of persistent CIS, new CIS, new high-grade papillary disease), development of T2 or greater or metastatic disease, cystectomy and death will be summarized for the FAS, and the subgroups with CIS and papillary only disease.

Kaplan-Meier methods will be used to estimate the EFS (ie, percent surviving without a recurrence) and the 95% confidence interval at 12, 24, 36, 48, 72, and 96 weeks in all patients in the FAS and the subgroup of patients with CIS. The median EFS (ie, median time to recurrence) and its 95% confidence interval will also be estimated. Kaplan-Meier plots for EFS will be created.

A sensitivity analysis will also be performed to analyze EFS using binomial methods where patients are considered as being recurrence-free if they have documented recurrence-free survival by the specified time point. Only evaluable patients will be included in the analysis. Patients will be considered evaluable if they have enough follow-up to determine recurrence status at the time point being summarized or if they have discontinued treatment. Exact 95% confidence intervals for EFS will be calculated.

This document is confidential.

A sensitivity analysis for EFS will be performed where if a patient missed a visit and at the next visit he/she experienced a recurrence, the recurrence will be counted from the day of the missed assessment. An additional sensitivity analysis will be performed where recurrence of any NMIBC, including low-grade disease, is counted as an EFS event.

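### SAP 7.3.2.2 counts nodal and distant disease as main progression where SAP 5.1.2 and the protocol do not, and the SAP 7.3.2.1 recurrence definition omits muscle-invasive, nodal and metastatic disease

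*SAP*

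**What the plan says.** **Progression.** Protocol 13.5.3 reads: "Progression is defined as the development of T2 or greater disease". The Protocol synopsis, Protocol 11.2 and SAP 5.1.2 use the same definition. SAP 5.1.2 then adds: "Sensitivity analyses will also be performed and will include any of the following as progressions". The list that follows has four alternatives: a rise from Ta or CIS to T1, T2 or greater, nodal disease, and distant metastasis. SAP 7.3.2.2 instead writes: "Progression is defined as the development of T2 or greater disease, which includes lymph node disease and distant metastasis". Its sensitivity analysis is one "which also includes an increase in stage from Ta or CIS to T1 as a progression event", so nodal and distant disease are already in the main set. SAP 7.7 says that nothing departs from the protocol.

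**EFS and recurrence.** SAP 7.3.2.1 states: "EFS is defined as the time from first dose of study medication to the first recurrence of disease or death from any cause". It gives recurrence two limbs. The first is "Appearance of new high-grade disease (ie, new high-grade papillary disease or new CIS) or"; the second is failure to clear baseline CIS by the Week 12 cystoscopy. The same section says that, apart from high-grade recurrence, "development of T2 or greater or metastatic disease, cystectomy and death will be summarized for the FAS" and for the CIS and papillary-only subgroups. Protocol 9.4.3 says: "Patients who have recurred with high-grade papillary carcinoma or with metastatic disease will be considered treatment failures"; such patients are also withdrawn. Protocol 11.1 and SAP 5.1.1 describe recurrence more broadly, as reappearing, persistent or new high-grade disease.

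**Censoring.** The only rule written for these endpoints' recurrence component is the one for time to recurrence in SAP 7.3.2.1: a patient without a recurrence event is censored at the last assessment free of recurrence. EFS has no rule of its own.

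**The concern.** Two main PFS event sets are in force at once. A programmer working from SAP 5.1.2 and one working from SAP 7.3.2.2 could produce different main PFS and time-to-progression results from the same data. In an open-label, single-arm study, the choice could be made after outcomes are known.

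The recurrence definition raises a second problem. EFS is meant to measure survival free of high-grade failure, but the operative list leaves out the most serious failures: muscle invasion, nodal spread and metastasis. A patient whom the protocol withdraws as a treatment failure could therefore enter the time-to-recurrence analysis as a censored observation. Leaving such patients uncounted favours the product.

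**Working it through.** The documents state no event rate or figure for this point, so there is nothing to reproduce. The check is a comparison of the texts, followed by the size of effect per patient.

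**1. Is SAP 7.3.2.2 only a clarification of T2 or greater?** Two things in the documents speak against it. Protocol Table 9.1 places T2 to T4 under the primary tumor and gives nodes and metastasis their own columns. The sensitivity lists in Protocol 11.2 and 13.5.3 and SAP 5.1.2 also name T2 or greater, nodal disease and distant metastasis as separate alternatives; if T2 or greater already covered the other two, those entries would be redundant. The main event sets therefore differ:

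| Event | Protocol 11.2, 13.5.3; SAP 5.1.2 | SAP 7.3.2.2 |
|---|---|---|
| T2 or greater | main | main |
| Nodal disease | sensitivity only | main |
| Distant metastasis | sensitivity only | main |
| Ta or CIS to T1 | sensitivity only | sensitivity only |

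**2. Follow one patient.** Take a patient with distant metastases, no new bladder lesion, CIS (if any) cleared by Week 12, and still alive.

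- PFS under SAP 7.3.2.2: event.
- Main PFS under SAP 5.1.2 and the protocol: no event.
- EFS under SAP 7.3.2.1: neither recurrence limb is met, so there is no event at that time; a later death would be one.
- Time to recurrence under SAP 7.3.2.1: censored at the last recurrence-free assessment.
- Protocol 9.4.3: treatment failure, withdrawn. It names metastatic disease but not nodal disease.

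**3. Size per patient, crude rate.** Inputs: 140 treated patients, of whom 70 to 100 have CIS (Protocol 13.1, SAP 7.1.5). The shift for k reclassified patients is 100 × k/N.

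- k = 1: 0.71 points at N=140, 1.00 at N=100, 1.43 at N=70.
- k = 3: 2.14, 3.00 and 4.29 points.
- k = 5: 3.57, 5.00 and 7.14 points.

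**4. Size in a Kaplan-Meier estimate.** This is an illustration with assumed counts: N=140; 60, 12, 8 and 5 high-grade events at Weeks 12, 24, 36 and 48; and k further patients with metastases only at Week 24.

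- If they count as events, 48-week EFS = (140 − 85 − k)/140.
- If they are censored at Week 24, 48-week EFS = (80/140) × (68/80) × (55 − k)/(68 − k).
- k = 1: 38.57% against 39.15%, a difference of 0.58 points.
- k = 3: 37.14% against 38.86%, a difference of 1.71 points.
- k = 5: 35.71% against 38.55%, a difference of 2.83 points.

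The Kaplan-Meier shift is smaller than the crude one in each case: 0.58 against 0.71, 1.71 against 2.14, and 2.83 against 3.57.

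**The case against.** The strongest defence has several parts, and much of it stands.

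- **A reader might infer that metastatic disease is never an EFS event.** The documents do not support that. The broader recurrence wording in Protocol 11.1 and SAP 5.1.1 could plausibly cover a new T2 or greater bladder tumor, Protocol 9.4.3 makes metastatic disease a treatment failure, and death from any cause is an EFS event. The texts conflict; they do not exclude these events everywhere. Death may not close the gap, however: Protocol 9.6 specifies 30 days of safety follow-up after treatment stops, so a later death may not be captured.
- **A reader might infer that such a patient is censored for EFS.** The written rule covers time to recurrence only. In the binomial EFS sensitivity analysis, patients who have discontinued treatment are evaluable and count as recurrence-free only if that is documented by the time point. A withdrawn patient would probably count against EFS there, so the two EFS methods could disagree.
- **A reader might infer that the EFS curve could lie above the PFS curve.** That is implausible. Under the plan's own alternatives, 70 CIS patients at a 40% CR rate leave 42 non-responders (42/140 = 30%), and 100 at 35% leave 65 (65/140 = 46%). Uncleared CIS is an EFS event. Not every non-responder has uncleared CIS, but these events would far outnumber the few patients at issue. The inconsistency is within individual patients.
- **The worst outcomes do not vanish from the report.** SAP 7.3.2.1 tabulates T2 or greater or metastatic disease, cystectomy and death separately.
- **The PFS gap is narrow.** The sensitivity event set in SAP 7.3.2.2 equals the protocol's. Only the analysis of T2 or greater alone is lost, and the SAP 7.3.2.2 main definition is the conservative one because it counts more events.
- **Such patients may seldom be recorded.** The schedules contain no follow-up imaging for nodal or distant disease, and the chest x-ray is at baseline only.

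None of this settles which main progression definition applies, or whether these failures are EFS events.

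**Conclusion.** The point holds as an inconsistency between definitions that affects PFS, time to progression, EFS and time to recurrence. The primary CR rate, its power and the interim rule are untouched. The two PFS definitions and the undeclared difference are plain in the text. So is the omission from the recurrence list, which on a literal reading censors a metastatic treatment failure in the time-to-recurrence analysis.

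The size rests on a patient count that the documents do not give. If one assumed that 2% to 5% of 140 (3 to 7 patients) were affected, the crude shift would be 2.1 to 5.0 points, but nothing in the plan supports that rate. What can be said is about 0.7 points per patient at N=140, 1.0 to 1.4 points in 100 to 70 CIS patients, and somewhat less by Kaplan-Meier. For EFS and time to recurrence, not counting these patients is the favourable direction. For PFS, that applies only if the narrower definition in SAP 5.1.2 and the protocol is programmed. The wording should be corrected before analysis.

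**What to change.** 1. Use one main progression definition in SAP 5.1.2 and 7.3.2.2, preferably T2 or greater, nodal or distant disease, with upstaging to T1 as the sensitivity analysis. Declare the difference from the protocol in SAP 7.7. Aligning SAP 7.3.2.2 with the protocol would also remove the conflict. Either way, it can be settled in the SAP without a protocol amendment.
2. In SAP 7.3.2.1, count muscle-invasive, nodal or metastatic urothelial cancer as an EFS and time-to-recurrence event. Keep the existing exceptions for tumor confined to the upper tract or prostatic urethra. Because the section requires recurrence to be biopsy proven, state what evidence is accepted for nodal and distant disease.
3. Add an explicit censoring rule for EFS, alongside the one for time to recurrence.

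The cost is SAP wording and the matching programming. The downside is that EFS, time to recurrence and PFS may come out slightly less favourable.

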7.3.2.3 Overall Survival

OS is defined as the time first dose of study medication until death. Kaplan-Meier methods will be used to estimate the OS (ie, percent surviving without death) and the 95% confidence interval at 48, 72, and 96 weeks in all patients in the FAS and the subgroup of patients with CIS. The median OS and its 95% confidence interval will also be estimated. Kaplan-Meier plots for OS will be created.

7.3.2.4 Quality of Life

Quality of life will be assessed using the EORTC QLQ-C30 (a general questionnaire for cancer) and the QLQ-NMIBC24 (a specific questionnaire for NMIBC disease). The questionnaire is administered at baseline (Day 1) and Weeks 21 and 45 prior to any clinical measurements, assessments, evaluations, or procedures being performed.

The QLQ-C30 is composed of both multi-item scales and single-item measures. These include five functional scales (physical, role, emotional, cognitive, and social), three symptom scales (fatigue, nausea and vomiting, and pain), a global health status/quality of life scale, and six single items (dyspnea, insomnia, appetite loss, constipation, diarrhea, and financial difficulties). Each of the multi-item scales includes a different set of items and no item occurs in more than one scale.

Each scale will be summarized on a 0-100 scale according to the scoring manual ([Fayers](#)). For functional scales and the global health status/quality of life scale, a higher score corresponds to greater function or quality of life. For symptom scales, a higher score corresponds to greater symptom burden.

This document is confidential.

The QLQ-NMIBC24 is composed of both multi-item scales and single-item measures related to NMIBC. These include five multi-item symptom scales (urinary symptoms, malaise, future worries, bloating and flatulence, and male sexual problems), one multi-item functional scale (sexual function) and five single-item measures (intravesical treatment issues, sexual intimacy, risk of contaminating a partner, sexual enjoyment, and female sexual problems).

Each scale in the QLQ-NMIBC24 will be summarized on a 0-100 scale similar to the scoring described for the QLQ-C30 ([Fayers](#); [Blazebury](#)). For functional scales (sexual function and sexual enjoyment), a higher score corresponds to greater function or quality of life. For symptom scales, a higher score corresponds to greater symptom burden.

Each scale from the two questionnaires will be summarized descriptively at baseline and the subsequent visits using the actual score at the visit and the change from baseline at the visit. Means, standard deviations, medians, range, and the 95% confidence interval for the mean will be summarized.

7.4 Safety Analysis

Safety will be assessed by evaluation of AEs and clinical laboratory results. All safety analyses will be performed using FAS.

7.4.1 Adverse Events

Adverse events will be graded according to the NCI CTCAE Version 5.0, coded using the MedDRA coding system, and displayed in tables and data listings by system organ class (SOC) and preferred term (PT).

A TEAE is any AE occurring after start of study medication or pre-existing medical condition that worsens in intensity after start of study medication and within 30 days of the last administration of study medication or is deemed to be related to study medication. AEs that occur after 30 days of the last administration of study medication and are not related to study medication will not be considered TEAEs.

All AEs occurring after the patient signs the ICF will be recorded, but only the TEAEs will be summarized in tables. AEs occurring between signing of the ICF and start of study medication will be included in separate listings from TEAEs.

If the start date of an AE is partially or completely missing, the date will be imputed using the rules specified in Section 7.1.3 to determine the treatment emergence. . The AE will be assumed to be treatment-emergent if it cannot be definitively shown that the AE did not occur or worsen during the treatment-emergent period (worst case approach).

Adverse events are summarized by patient incidence rates; therefore, in any tabulation, a patient contributes only once to the count for a given SOC or PT (i.e., the most related occurrence or the most intense occurrence). Missing relationship will be considered definitely related to BC-819.

An overall AE incidence summary table will be produced and will include:

- The number and percentage of patients reporting at least 1 TEAE
- The number and percentage of patients reporting at least 1 serious AE (SAE)
- The number and percentage of patients reporting at least 1 TEAE with toxicity grade of 3 or higher
- The number and percentage of patients reporting a TEAE leading to withdrawal of study drug

This document is confidential.

- The number and percentage of patients reporting a TEAE leading to study drug interruption
- The number and percentage of patients reporting a TEAE leading to death
- The number and percentage of patients reporting at least 1 TEAE related to treatment
- The number and percentage of patients reporting at least 1 treatment-related TEAE with toxicity grade of 3 or higher
- The number and percentage of patients reporting at least 1 treatment-related serious AE (SAE)
- The number and percentage of patients reporting a treatment-related TEAE leading to death

Tabulations by SOC and PT will be produced for all TEAEs, treatment-related TEAEs, SAEs, treatment-related SAEs, TEAEs Grade ≥ 3 (including columns for highest grade 3, 4, and 5), treatment-related TEAEs Grade ≥ 3 (including columns for highest grade 3, 4, and 5), TEAEs leading to study drug withdrawal, TEAEs leading to study drug interruption, treatment-related TEAEs leading to death and TEAEs, treatment-related TEAEs and SAEs by maximum toxicity grade. These will be presented by SOC and PT, sorted by decreasing frequency. The tabulations will be also be presented separately by PT, sort by decreasing frequency. All tabulations will be presented by overall patients. Additionally, overall summary, TEAEs, treatment-related TEAEs, TEAEs Grade ≥ 3 , treatment-related TEAEs Grade ≥ 3 , SAE, treatment-related SAE, treatment-related death will also be tabulated by patients with baseline CIS.

In addition to standard MedDRA SOC and PT tables of AEs, a composite class of urinary tract-related AEs will also be created and the incidence and severity of AEs in this composite class tabulated. SOC and PTs for urinary tract-related AEs are shown in Table 4.

Table 4 Urinary Tract–Related Adverse Events

System Organ Class	Preferred Term
Infections and infestations	Urinary tract infection
	Urosepsis
Investigations	Blood creatinine increased
Renal and urinary disorders	Any

No formal hypothesis-testing analysis of AE incidence rates will be performed. All AEs occurring on-study will be provided in data listings. By-patient listings also will be provided for the following: SAEs, AEs leading to study drug withdrawal, and AEs leading to study drug interruption.

